4. LIST OF ABBREVIATIONS

AOUI - Azienda Ospedaliera Integrata Universitaria AP-HP - Public Assistance Hospital of Paris BADL - Basic Activity of Daily Living BMI - Body Mass Index CBCI - Catholics Bishops Conference of India, Society for Medical Education, Bangalore, India; CERMEL - Lambaréné Medical Research Center CFQ - Cognitive Failure Questionnaire CFS - Clinical Frailty Scale CHARITÉ - University Medicine Berlin CI - Confidance Interval **CINECA** - Interuniversity Consortium CINES - National IT Center for Higher Education confidence interval Cis COVID-19 - COronaVIrus Disease 19 CRF - Clinical research form **CRO - Clinical Research Associate** CRP C-reactive protein CTCAE - According to Common Terminology Criteria for Adverse Events DLCO - Diffusion Lung CO ECG - Electrocardiograph eCRF - Electronic clinical research form EQ-5D-5L - EuroQol five-dimension five-level FCRM - Congolese Foundation for Medical Research FDA - Food and Drug Administration FEV - Forced Expiratory Volume FRC – Functional Residual Capacity FVC - Forced Vital Capcity GHI - Good Clinical Practice, GMBH HMGU - Helmholtz Zentrum Muenchen German Research Center for Health and Environment GPAQ - Global Physical Activity, Questionnaire HADS - Anxiety and Depression Scale HCW - Health Care Workers HIV - Human Immunodeficiency Virus HMGU - Helmholtz Zentrum Munchen ICF - Informal Consent Form ICH - Conference on Harmonisation ICMJE -International Committee of Medical Journal Editors ICU - Intensive Care Unit IES-R - Impact of Event Scale - Revised INR - International Normalized Ratio INSERM - Institut National de la Santé et de la Recherche Médicale INSP - National Institute of Public Health IQR - Interquartile Range IRB - Institutional Review Board IRB/IEC -- Institutional review board/inidipendent ethics ISGLOBAL-Barcelona Private Foundation Global Health Institut K10 - Kessler Psychological Distress Scale LCTF - Long term care facilities

LEOSS - Lean European Open Survey on SARS-CoV-2 Infected Patients LIH-Luxembourg Institute of Health LMU MUENCHEN - Ludwig-Maximilians-University Munich LTCF – Long Term Care LURM Laboratorio Universitario di Ricerca Medica mMRC - Modified Medical Research Council MOS SF - Medical Outcome Study Short Form (MOS SF)-36 Score, MRI - Magnetic Resonance Imaging MRI - Magnetic Resonance Imaging PCFS - Post-COVID-19 Functional Status Scale, PCR- polymerase chain reaction PENTA foundation - for the treatment and care of children with HIV and related diseases - ONLUS USTUTT - University of Stuttgart PI - Principal Investigator RAPH BB - Regional Office of Public Health with its seat in Banská Bystrica REG VEN-Veneto region **RER-ASSR** Emilia Romagna region RT-PCR - reverse transcriptase-polymerase chain reaction **RV-Residual volume** SAS-Andalusian Health Service SGRO - Saint George Respiratory Questionnaire SoA - Schedule of Assessment SOFA-Sequential[Sepsis-Related]Organ Failure Assessment Score TDI - Transition Dyspnoea Index THSTI - Translational Health Science and Technology Institute, Faridabad, Haryana, India; TLC – Total Lung Capacity **UANTWERPEN - University of Antwerpen** UBA - Universidad de Buenos Aires UHC - Clinic of the University of Cologne UMCG - University Medical Center Groningen UNIBO - University of Bologna UNIOVI - University of Oviedo UNIVR- University of Verona WGS – Whole genome sequencing WES – Whole exome sequencing WP-Work Package

5. BACKGROUND

The ongoing COVID-19 pandemic has created a global public health emergency that is challenging societies, health care systems and national economies worldwide [1]. Since the beginning of the pandemic, our knowledge of transmission dynamics [2], clinical presentation [3], long-term sequelae [4], and risk factors for disease progression [5-7] has been increasing steadily. Evidences on the efficacy of treatment strategies coming from clinical trials [8] have been obtained and preventive measures such as social distancing and vaccination campaigns, have been put in place. Nonetheless, there is still an urgent need for a more standardized research activity, connecting multiple countries and settings and focusing on the different aspects of this pandemic. High-quality data and biological samples collection coming from large multicentric cohorts are urgently required and have not yet been implemented in an international level. Evidence-based knowledge is required to enable rapid and effective decision-making, with particular attention to the transferability of the collected information.

COVID-19 can result in prolonged illness, even in young adults and children without underlying chronic medical conditions. In a telephone survey conducted by the Centers for Disease Control and Prevention among a random sample of 292 adults (≥18 years) who had a positive outpatient test result for SARS-CoV-2 by RT-PCR, 35% of 274 symptomatic respondents reported not having returned to their usual state of health 2 weeks or more after testing [9]. The burden of COVID-19 long-term sequelae and the exact underlying pathophysiology mechanisms remain unknown. Results from the follow-up of large cohorts are particularly needed to fully understand the characteristics and risk factors for SARS-CoV-2 infection long-term consequences.

From the point of view of the social science, this study will allow investigating two largely unexplored issues. On one hand, there is a need to dig into the determinants of adherence to preventative strategies, including non-pharmacological measures and vaccines. The lack of knowledge is particularly large among individuals who have experienced SARS-CoV-2 infection due to the possibility of re-infection and of infection transmission to others. On the other hand, there is a lack of knowledge on the use of health system resources SARS-CoV-2 infection implies across different settings and resources availability: length of hospital stay, frequency of follow-up visits, for example, have been projected at the start of the pandemic but the actual figures constitute unexplored information.

The present study is part of ORCHESTRA project, a three-year international research project aimed at tackling the coronavirus pandemic. ORCHESTRA provides an innovative approach to learn from the pandemic SARS-CoV-2 crisis, derive recommendations to further management of COVID-19 and be prepared for the possible future pandemic waves. The ORCHESTRA project aims to deliver sound scientific evidence for the prevention and treatment of the infections caused by SARS-CoV-2 assessing

epidemiological, clinical, microbiological, and genotypic aspects of population, environment and socioeconomic features. The project builds upon existing, and new largescale population cohorts in Europe (France, Germany, Spain, Italy, Belgium, Romania, Netherlands, Luxemburg, and Slovakia) and non-European countries (India, Perú, Ecuador, Colombia, Venezuela, Argentina, Brazil, Congo and Gabon) including SARS-CoV-2 infected and non-infected individuals of all ages and conditions. The primary aim of ORCHESTRA is the creation of a new pan-European cohort applying homogenous protocols for data collection, data sharing, sampling, and follow-up, which can rapidly advance the knowledge on the control and management of the COVID-19. ORCHESTRA will include SARS-CoV-2-negative individuals and thereby enable a prospective follow-up and an analysis of vaccination response. The cohort will involve all patients with SARS-CoV-2 infections including fragile individuals (children, elderly, transplanted, oncological, HIV infected, and those with Parkinson disease or rheumatologic disease) if followed up in one of the study Partners center. Within ORCHESTRA project, the Work Package 2 (WP2) aims to assess long-term sequelae in recovered COVID-19 individuals. The scope of the present protocol is to describe the procedures of the long-term follow-up of COVID-19 patients enrolled in ORCHESTRA cohorts.

6. STUDY RATIONALE

The present protocol, in accordance with the objectives of ORCHESTRA project - Work Package 2, aims at investigating the characteristics and determinants of COVID-19 long-term sequelae. This goal will be reached through the harmonization of follow-up strategies across the participating cohorts to allow a standardized collection of data on COVID-19 long-term sequelae. The result will be a platform including a set of data and biomaterials from large scale international cohorts, that will be uniformly recorded, prospectively tracked and analysed with the ultimate goal of providing evidence which will contribute to the optimization and improvement of the management of COVID-19 sequelae and to their prevention.

The follow-up will be organized in multiple levels of tests according to the capability of each cohort and will include questionnaires to collect demographic, epidemiological and clinical data, physical examination, radiological exams and biological sampling. The long-term follow-up will also allow the assessment of long-term immunological response to SARS-CoV-2 infection and its association to different treatment strategies, including monoclonal antibodies and vaccination.

7. STUDY DESIGN

This is a multicenter, observational, prospective cohort study investigating COVID-19 sequelae in hospitalised and non-hospitalised patients up to 18 months after the diagnosis of SARS-CoV-2 infection. The present study is conceived, at the coordinating center of UNIVR, as an extension of the study "Biobanca associata a banca dati dei casi di COVID 19 gestiti presso l'Azienda Ospedaliera Universitaria di Verona" (COVID-19-VR), which was started in April 2020 at the Verona University Hospital to assess the long-term effects of COVID-19 on mental, respiratory, and functional status through the administration of questionnaires (CESC 2577). Patients will be recruited in multiple European and non-European countries, accounting for the participation of approximately 10000 individuals in the prospective follow-up data collection.

Recording of clinical data, administration of questionnaires, collection of biological samples and imaging will take place at fixed time-points to allow a comprehensive follow-up of COVID-19 patients. The follow-up will include two levels of assessments: the first one is mandatory, the second one will be customized according to the feasibility of each cohort. A detailed overview of the schedule of the study visits and the clinical variables to be recorded is shown in Table 1. An ad hoc database will be provided to each COVID-19 cohort involved to allow homogeneous and standardised data collection.

8. OBJECTIVES

Main objectives of the study are:

- To describe characteristics of COVID-19 sequelae, including type, rate, and length through clinical, laboratory, and radiological assessments
- To investigate valuable, confounder-adjusted, associations between COVID-19 sequelae and COVID-19 severity, comorbidities, aetiology (SARS-CoV-2 variants), COVID treatment (including monoclonal antibodies), and trends in SARS-CoV-2 antibodies
- To describe the rate, the aetiology (SARS-CoV-2 variants), severity, and clinical determinants of COVID-19 re-infections

Furthermore, data retrieved from COVID-19 cohorts will address the following objectives:

- To compare the time course of the immunological response of the population with sequelae with the immunological response of the population without sequelae.
- To investigate immunological patterns related to specific long-term sequelae.

- To investigate possible associations of SARS-CoV-2 variants with COVID-19 severity, time course of the immunological response, and long-term sequelae.
- To describe the rate and severity of sequelae and immunological trends of COVID-19 in patients vaccinated against SARS-CoV-2.
- To describe the time course of intestinal and pulmonary microbiome after SARS-CoV-2 infection.
- To investigate possible associations of long-term sequelae with hypercoagulability
- To describe the relationship between risk perception of reinfection and the adherence to preventative measures over time after the SARS-CoV-2 infection, including vaccine acceptance.
- To describe the use of health care services among patients recovered from SARS-CoV-2.
- To identify human and viral genetic markers indicative of disease severity using WGS or WES followed by functional analysis of the most promising variants.

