1.2		1	1	ı					

Elderly					
Cognitive status ²⁷	Х	Х	Х	Х	Х
Pregnant women/new mother					
History of positive SARS-CoV-2					
molecular test on amniotic fluid or					
breast milk ²⁸					
History of detection of micro-					
thrombotic disease on placenta tis-					
sue or umbelical cord tissue					
Children					
History of positive SARS-CoV-2					
molecular test on amniotic fluid or					
breast milk ²⁸					
Biometric paramethers ²⁹	Х	Х	Х	X	Х
Transplant					
Transplant general information ³⁰					
Graft function ³¹	Х	Х	Х	Х	Х
Immunosuppressive regimen ³²	Х	Х	Х	Х	Х
Onco-haematology					
Assessment of adherence to onco-	Х	х	X	х	х
logic follow-up visits and therapy	Λ	Λ	Λ	Λ	Λ
Assessment of progression of the	Х	X	x	х	х
disease and relapse	Λ	Λ	Λ	Λ	Λ
Assessment of adverse events ³³	Х	Х	Х	Х	Х

Footnotes

Modular data capture according to level of commitment (level I, level II, level III).

Level I	Assessments in level I are mandatory
Level II	Customized according to the feasibility of each cohort

- * Reassessed only if outside the normal ranges at the previous assessment or if clinically indicated
- 1. Day 0: first positive SARS-CoV-2 test
- Demographics: age (years), sex, ethnic group (African, Asian, European, Latin America...), education (no formal education, lower than college, college or higher), cigarette smoking (never-smoker, former smoker, current smoker), usual residence (home, long-term care facility, public dormitory, prison, homeless), current occupation (student, unemployed with no benefits, unemployed with benefits, employed, self-employed, informal worker)
- 3. Healthcare setting: (a) outpatient (b) non-intensive care unit (c) intensive care unit.
- 4. Medical history: cardiovascular diseases (hypertension, coronary artery disease, congestive heart failure), diabetes (without insulin, with insulin), chronic respiratory disease (asthma, chronic ob-

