structive pulmonary disease, obstructive sleep apnoea, restrictive lung disease, pulmonary hypertension), kidney disease (chronic with/without dialysis), liver disease other than cancer (HBV/HCV/HDV chronic viral hepatitis, other chronic disease, cirrhosis), metabolic disease, immunosuppressive conditions (solid organ transplant recipient, auto-immune diseases), cancer (solid cancer, haematological malignancies, type of primitive cancer/haematological malignancies, presence of metastases, if ongoing chemotherapy), mental or neurological disorders (psychiatric illness, anxiety disorder, mood disorder, psychotic disorder, Alzheimer disease, dementia other than Alzheimer, Parkinson's disease, myasthenia gravis, epilepsy, stroke (with/without residual deficits, neuromuscular disease, multiple sclerosis), muscular dystrophy, amyotrophic lateral sclerosis); TB co-infection; other opportunistic co-infection (specify) for HIV population

- 5. Comorbidity management: drug name and dose (to include only treatments taken regularly)
- 6. Anti-COVID therapy: drug name, maintenance dose, and duration
- 7. Antibiotic therapy: drug name, dose, duration, and type of treated infection
- Oxygen therapy: nasal prongs, face mask, face mask with reservoir, high-flow nasal cannula, noninvasive ventilation, mechanical ventilation; numbers of O₂ (L/min) provided (maximum reached) and fraction of inspired O₂ (FiO₂) provided (maximum reached)
- 9. SARS-CoV-2 vaccination: vaccine name, date of administration
- Relevant new medical events or worsening of previous conditions, including deep venous thrombosis, pulmonary embolism, infections (including a new SARS-CoV-2-infection during follow-up), malignancies (type of cancer, overall stage).
- 11. Symptoms: abdominal pain, ageusia/dysgeusia, anosmia, balance impairment, behaviour disorder, chest pain or chest tightness, confusion, cough, delirium, diarrhoea, disrupted sleep, dizziness, dysp-noea, fatigue, fever (including low-grade fever), headache, hypothermia, impaired cognitive status, lethargy, loss of appetite, mood affective disorder, myalgia, nausea/vomiting, palpitation, phlegm, runny nose, sore throat, stuffed nose, syncope, wheeze.
- 12. WHO Clinical Progression Scale
- 13. Vital signs: dead/alive, blood pressure, body temperature, heart rate, respiratory rate, peripheral oxygen saturation

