13. STATISTICAL ANALYSIS

Sample size calculation. The number of inclusions will depend on the progress of the SARS-CoV-2 pandemic, which is unknown at this time. Therefore, the number of patients who will be included cannot be determined in advance. However, depending on the timing of the project and the included cohorts, the expected enrollment is 10000 subjects.

We will carry out comprehensive descriptive analyses taking into account sociodemographic factors and clinical courses. The frequency distributions of the characteristics will be given in absolute and relative numbers, median plus interquartile range (IQR) or mean values plus 95% confidence interval (CIs). Associations with specific treatment strategies, disease severity patterns and laboratory results will be analysed using chi-square tests, t-tests or Mann-Whitney tests, depending on the data. To evaluate potential risk factors, multivariate regression models will be carried out. Outcome time analyses using Cox proportional-hazards regression models with time-dependent covariates will be performed to examine

factors associated with each endpoint (including death). In addition, we will use cumulative incidence functions, such as the Fine-Gray subdistribution hazard regression model, to account for competing events (i.e., relocation, discharge against medical advice, etc.). For missing values, a different strategy to understand the causes and the significance for the analysis will be developed and a graduated procedure for dealing with censorship and imputations via linked regressions will be developed. The significance level is defined with a p-value <0.05. All statistical analyses will be carried out with STATA, Python and/or R statistics software by trained staff (epidemiologists, statisticians) using the latest analysis methods.

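### The plan does not separate vaccination before Day 0 from vaccination after it, or say how titres after a vaccine dose or monoclonal antibody are handled, so unadjusted antibody comparisons may be confounded by vaccination

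*Combined protocol and SAP*

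**What the plan says.** **Objectives (section 8).** One main objective is "To investigate valuable, confounder-adjusted, associations between COVID-19 sequelae and COVID-19 severity"; its list of factors runs on to "COVID treatment (including monoclonal antibodies), and trends in SARS-CoV-2 antibodies". Antibody trend is thus an exposure in a main, adjusted objective. Two further objectives bear on the point and promise no adjustment: "To compare the time course of the immunological response of the population with sequelae with the immunological response of the population without sequelae" and "To describe the rate and severity of sequelae and immunological trends of COVID-19 in patients vaccinated against SARS-CoV-2". None of the three places vaccination in time relative to infection.

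**Rationale (section 6).** The long-term immune response is to be studied together with "its association to different treatment strategies, including monoclonal antibodies and vaccination".

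**Data collected (section 3.2 and section 12).** Time zero is given as "Day 0: first positive SARS-CoV-2 test". Footnote 9 records "SARS-CoV-2 vaccination: vaccine name, date of administration". Section 12 makes vaccination status and SARS-CoV-2 antibodies mandatory at each follow-up visit. Anti-COVID therapy is scheduled at the acute visit only, and footnote 6 lists drug, maintenance dose and duration, without a date.

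**Analysis (section 13).** The one sentence that mentions laboratory results ends "laboratory results will be analysed using chi-square tests, t-tests or Mann-Whitney tests, depending on the data". Regression is planned for risk factors, without a covariate list. Cox models with time-dependent covariates are planned for outcome-time analyses, with no covariate named. Vaccination and monoclonal antibody do not appear in this section. No part of the document states an antibody target that would distinguish antibody from infection, from vaccine and from infusion.

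**The concern.** A vaccine dose or an infused monoclonal antibody can change the measured titre. Sampling runs to month 18, so many titres may be taken after such an event. If patients with and without sequelae differ in vaccine uptake, a crude comparison of their titres carries that difference and can be read as a difference in immune response to infection.

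Such a difference in uptake is plausible. Vaccination is voluntary, and footnote 21 of the schedule collects reasons for refusal, among them that the patient sees no use for it in their own case. The timing will also be mixed: one contributing cohort was hospitalised from March 2020 (section 9.7), while recruitment runs to January 2023 (section 11).

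The vaccinated-patients objective has a related problem. Infection after vaccination and vaccination after infection are different situations. A single rate of sequelae over both depends on how many patients of each kind happen to be enrolled.

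**Working it through.** The plan gives no figure on this point to reproduce. The expected enrolment of 10000 is stated without an effect size or power. The calculations below are illustrations. From the documents they take 10000, the 0.05 level (two-sided assumed) and 35% with sequelae; the 35% comes from the outpatient survey in section 5 and not from this cohort. Everything else is assumed.

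**1. Size of the false ratio.** Let a dose raise the titre by b on the log10 scale, and let the vaccinated share at a visit differ by g between patients with and without sequelae. With no true difference in response to infection, the crude geometric mean ratio is 10^(b × g).

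| b | g | Ratio |
|---|---|---|
| 1.0 (10-fold) | 0.10 | 10^0.10 = 1.26 |
| 1.0 | 0.05 | 10^0.05 = 1.12 |
| 0.5 | 0.10 | 10^0.05 = 1.12 |
| any | 0 | 1.00 |

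**2. How large g can be.** For a given vaccination–sequelae odds ratio (OR), the largest possible gap is (1 − √OR)/(1 + √OR).
- OR 0.7: (1 − 0.837)/(1 + 0.837) = 8.9 points.
- OR 0.5: (1 − 0.707)/(1 + 0.707) = 17.2 points.
- Conversely, OR = ((1 − g)/(1 + g))². A 10-point gap needs an OR of at most (0.9/1.1)² = 0.67, or its reciprocal. Gaps of 20 and 30 points need (0.8/1.2)² = 0.44 and (0.7/1.3)² = 0.29.

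**3. False-positive rate of a crude comparison.** Assumptions: log10 titre SD 0.5 within vaccination group, b from 0.5 to 1.0, 20 to 80% vaccinated, and no true antibody effect.

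| Vaccination–sequelae OR | N = 1000 | N = 10000 |
|---|---|---|
| 1.0 | 5% | 5% |
| 0.9 | 6 to 9% | 12 to 43% |
| 0.7 | 12 to 47% | 68 to 100% |
| 0.5 | 30 to 95% | 99.5 to 100% |

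**4. Effect of adjustment.** In 400 simulated cohorts (N = 10000, 50% vaccinated, b = 1.0, OR 0.7), a logistic model of sequelae on titre alone rejected in 100% of runs, with a false OR of 0.84 per log10. Adding vaccination before the titre as a covariate brought rejection to about 3% and the OR to 1.00. With OR 1.0, rejection was 3.3% crude and 5.8% adjusted, so there was no bias to remove.

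**5. Pooling the two vaccinated groups.** Suppose vaccination after infection leaves the rate at 35%, and vaccination before it has OR 0.6. The second rate is then 0.323/1.323 = 24.4%, since 0.6 × 0.35/0.65 = 0.323. The pooled rate is 0.1 × 24.4 + 0.9 × 35 = 33.9% if 10% were vaccinated before Day 0, and 0.9 × 24.4 + 0.1 × 35 = 25.5% if 90% were. The same two risks give different pooled results according to the mix.

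**The case against.** The strongest reply is that the plan is silent rather than wrong. Section 13 names no covariates for any analysis. The main antibody objective is to be confounder-adjusted, regression and time-dependent covariates are foreseen, and section 6 shows that vaccination and monoclonal antibodies are recognised as relevant to the immune response. Dose dates and Day 0 allow before and after to be derived. All of this is correct, and it rules out three stronger readings that a reader might infer.

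- *That the plan decides to pool, so that antibody associations will reflect vaccination.* No such decision is written. Bias needs vaccination to differ by sequelae status and to be left unadjusted; without that difference, the crude error rate stays at 5%.
- *That vaccinated patients gain a false advantage from having survived and stayed in follow-up until their dose.* This needs an unvaccinated comparator. The vaccinated-patients objective is descriptive and states none. It can even be read as covering only people infected after vaccination.
- *That false ratios of 1.58 or 2.0 (gaps of 20 or 30 points with a 10-fold boost) are to be expected.* By step 2 they need odds ratios of about 0.44 and 0.29, which are strong associations.

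The reply does not close the gap. The adjustment promise belongs to the main objective only and names no confounder. The time-dependent covariates are tied to outcome-time models and not to titre trajectories. For the immune time-course comparison, the only stated methods that refer to laboratory results are crude tests. Dates that make a split possible do not commit analysts across several cohorts to making it in the same way.

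**Conclusion.** The concern holds in a limited form. The plan leaves undefined the timing of vaccination relative to Day 0 and the handling of titres after a vaccine dose or monoclonal antibody. If the named crude tests are followed, the comparison of immune time course by sequelae status may be confounded by vaccination, and the vaccinated-patients description may mix two groups. For the main antibody objective the gap is narrower: adjustment is promised, but not for what.

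The size depends on assumptions that the documents cannot settle. A ratio of about 1.26 needs a 10-fold boost and a 10-point gap, and that gap in turn needs a vaccination–sequelae odds ratio of about 0.67 or stronger. Half the boost on the log scale, or half the gap, gives 1.12. At the expected enrolment even small distortions could reach significance: 12 to 43% false positives at an odds ratio of 0.9, if all 10000 contribute titres. This should be settled before analysis.

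**What to change.** 1. Define two vaccination variables: before Day 0 (fixed) and after Day 0 (time-dependent from the recorded dose date). Report the vaccinated-patients objective separately for the two groups.
2. For antibody analyses, replace the crude tests with a longitudinal regression of titre that includes time-varying terms for post-infection vaccination and for monoclonal antibody, as well as vaccination before Day 0. Name these among the confounders for the main antibody objective.
3. As a sensitivity analysis, restrict to samples taken before any post-infection dose or monoclonal antibody. This should not be the main analysis. If patients choose vaccination according to symptoms, the restriction is informative. Because anti-COVID therapy is recorded at the acute visit, it would also remove most follow-up titres of patients given monoclonal antibodies, whom the objectives single out for study.
4. State the antibody target of the assay.
5. Confirm that the eCRF holds the date of monoclonal antibody administration. Footnote 6 does not list it, but the eCRF itself may.

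The cost is a few sentences in section 13, slightly more analysis work, possibly one eCRF field, and fewer late titres in the sensitivity analysis. Vaccination dates are already collected.
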